7.2.3 Blinded Phase

7.2.3.1 Visit 3 (Week 4 ± 7 days)

- Collect the used tubes of study medication from the subject (or parent/guardian) and weigh the tubes.
- Collect and review the dosing diary.
- Review any concomitant medication used since the previous study visit.
- Measure vital signs (systolic and diastolic blood pressure, heart rate, and respiratory rate) with subject in a seated position.
- Obtain blood samples and optional urine samples for a laboratory profile including hematology, clinical chemistry, and urinalysis.
- Obtain blood sample for pharmacokinetic analysis.
- Perform a UPT for females of childbearing potential. Remind sexually-active female subjects of childbearing potential to use approved method(s) of contraception. Remind sexually active male subjects that they (or their female partners) should use appropriate contraception. (In the unlikely event that a urine pregnancy test cannot be obtained, a serum pregnancy test can be run from the serum sample collected.) (For China, different pregnancy test procedure would be followed).
- Perform the following efficacy assessments:
 - Investigator's Global Assessment (IGA);
 - Facial Angiofibroma Severity Index (FASI) (assessment of erythema, size, and extension);
 - Modified Nobel Scoring System (assessment of target lesions and non-target lesions response);
 - Categorical lesion count using the following categories: (0) no lesion; (1) <25 lesions; (2) 25-50 lesions; (3) 51-75 lesions; (4) >75 lesions.

- Assessment of lesion elevation.
- Have the subject (or parent/guardian for subjects under the developmental age of 7 years) complete the subject self-assessment survey.
- Take a photograph of the angiofibroma according to the Standardized Operation Procedure (Appendix 2).
- Record any AEs.
- Weigh the study medication and dispense to the subject (or parent/guardian).
- Dispense the dosing diary to the subject.
- Schedule the next study visit; instruct the subjects (or their parent/guardian) to bring the study medication to the study visit.

7.2.3.2 Telephone Visit 4 (Week 8 ± 7 days)

- Review any concomitant medication used since the previous study visit.
- Record any AEs.
- Assess subject's compliance with study medication.
- Assess subject's compliance with maintaining the dosing diary.
- Schedule the next visit; instruct the subject (or parent/guardian) to bring the study medication to the study visit.

7.2.3.3 Visit 5 (Week 12 ± 7 days)

- Collect and review the dosing diary.
- Collect all study materials from the subject (or parent/guardian), including unused study medication, etc.
- Weigh the used tubes of study medication collected from the subject (or parent/guardian).
- Review any concomitant medication used since the previous study visit.
- Measure vital signs (systolic and diastolic blood pressure, heart rate, and respiratory rate) with subject in a seated position.
- Obtain blood samples and optional urine samples for a laboratory profile including hematology, clinical chemistry, and urinalysis.
- Perform a UPT for females of childbearing potential. Remind sexually-active female subjects of childbearing potential to use approved method(s) of contraception. Remind sexually active male subjects that they (or their female partners) should use appropriate contraception. (In

the unlikely event that a urine pregnancy test cannot be obtained, a serum pregnancy test can be run from the serum sample collected.) (For China, different pregnancy test procedure would be followed).

- Perform the following efficacy assessments:
 - Investigator's Global Assessment (IGA);
 - Facial Angiofibroma Severity Index (FASI) (assessment of erythema, size, and extension);
 - Modified Nobel Scoring System (assessment of target lesions and non-target lesions response);
 - Categorical lesion count using the following categories: (0) no lesion; (1) <25 lesions; (2) 25-50 lesions; (3) 51-75 lesions; (4) >75 lesions;
 - Assessment of lesion elevation.
- Have the subject (or parent/guardian for subjects under the developmental age of 7 years) complete the subject self-assessment survey.
- Take a photograph of the angiofibroma according to the Standardized Operation Procedure (Appendix 2).
- Record any AEs.
- If subject will not be participating in the open-label treatment period, schedule the End of Study Visit.
- If the subject will be participating in the open-label treatment period:
 - Subject must have completed the double-blind treatment period, with an overall compliance rate that is > 80%, as determined by the dosing diary.
 - Weigh the open-label study medication and dispense to the subject or their parent/guardian.
 - Dispense the dosing diary to the subject.
 - Schedule the next visit; instruct the subject to bring the study medication to the study visit.

7.2.4 Open-label Phase

7.2.4.1 Visit 6 (Week 16 ± 7 days)

- Collect the used tubes of study medication from the subject (or parent/guardian) and weigh the tubes.
- Collect and review the dosing diary.

- Review any concomitant medication used since the previous study visit.
- Measure vital signs (systolic and diastolic blood pressure, heart rate, and respiratory rate) with subject in a seated position.
- Obtain blood samples and optional urine samples for a laboratory profile including hematology, clinical chemistry, and urinalysis.
- Perform a UPT for females of childbearing potential. Remind sexually-active female subjects of childbearing potential to use approved method(s) of contraception. Remind sexually active male subjects that they (or their female partners) should use appropriate contraception. (In the unlikely event that a urine pregnancy test cannot be obtained, a serum pregnancy test can be run from the serum sample collected.) (For China, different pregnancy test procedure would be followed).
- Perform the Investigator's Global Assessment (IGA).
- Perform the Modified Nobel Scoring System (assessment of target lesions and non-target lesions response).
- Have the subject (or parent/guardian for subjects under the developmental age of 7 years) complete the subject self-assessment survey.
- Take a photograph of the angiofibroma according to the Standardized Operation Procedure (Appendix 2).
- Record any AEs.
- Weigh the study medication and dispense to the subject (or parent/guardian).
- Dispense the dosing diary.
- Schedule the next visit; instruct the subjects (or parent/guardian) to bring the study medication to the study visit.

7.2.4.2 Telephone Visit 7 (Week 20 ± 7 days)

- Review any concomitant medication used since the previous study visit.
- Record any AEs.
- Assess subject's compliance with study medication.
- Assess subject's compliance with maintaining the dosing diary.
- Schedule the next visit; instruct the subjects (or parent/guardian) to bring the study medication to the study visit.

7.2.4.3 Visit 8 (Week 24 ± 7 days)

- Collect and review the dosing diary.
- Collect all study materials from the subject (or parent/guardian), including unused study medication, etc.
- Weigh the used tubes of study medication collected from the subject (or parent/guardian).
- Review any concomitant medication used since the previous study visit.
- Perform a physical examination, including height and weight.
- Measure vital signs (systolic and diastolic blood pressure, heart rate, and respiratory rate) with subject in a seated position.
- Obtain blood samples and optional urine samples for a laboratory profile including hematology, clinical chemistry, and urinalysis.
- Perform a UPT for females of childbearing potential. Remind sexually-active female subjects of childbearing potential to use approved method(s) of contraception. Remind sexually active male subjects that they (or their female partners) should use appropriate contraception. (In the unlikely event that a urine pregnancy test cannot be obtained, a serum pregnancy test can be run from the serum sample collected.) (For China, different pregnancy test procedure would be followed).
- Perform the following efficacy assessments:
 - Investigator's Global Assessment (IGA);
 - Facial Angiofibroma Severity Index (FASI) (assessment of erythema, size, and extension);
 - Modified Nobel Scoring System (assessment of target lesions and non-target lesions response);
 - Categorical lesion count using the following categories: (0) no lesion; (1) <25 lesions; (2) 25-50 lesions; (3) 51-75 lesions; (4) >75 lesions;
 - Assessment of lesion elevation.
- Take a photograph of the angiofibroma according to the Standardized Operation Procedure (Appendix 2).
- Have the subject (or parent/guardian for subjects under the developmental age of 7 years) complete the subject self-assessment survey.
- Record any AEs.

- Schedule the End of Study Visit.

7.2.5 Telephone End of Study Visit (14 ± 3 days after final dose of IP) – Both Blinded and Open-Label Participants

- Review any concomitant medication used since the previous study visit.
- Record any AEs.
- Inform Subjects that they may be approached to participate in future trials with this product.
- Dismiss the subject from the study.

7.2.6 Early Termination (Blinded and Open-Label)

If a subject withdraws from the study prior to the End of Study visit, the subject is to return to the site. The early termination procedures should be performed, as specified below:

- Collect all study materials from the subject (or parent/guardian), including used and unused study medication, subject dosing diary, etc.
- Weigh the used tubes of study medication collected from the subject.
- Review any concomitant medication used since the previous study visit.
- Perform a physical examination, including height and weight.
- Measure vital signs (systolic and diastolic blood pressure, heart rate, and respiratory rate) with subject in a seated position.
- Obtain blood samples and optional urine samples for a laboratory profile including hematology, clinical chemistry, and urinalysis.
- Perform a UPT for females of childbearing potential. Remind sexually-active female subjects of childbearing potential to use approved method(s) of contraception. Remind sexually active male subjects that they (or their female partners) should use appropriate contraception. (In the unlikely event that a urine pregnancy test cannot be obtained, a serum pregnancy test can be run from the serum sample collected.) (For China, different pregnancy test procedure would be followed).
- Perform the following efficacy assessments:
 - Investigator's Global Assessment (IGA);
 - Facial Angiofibroma Severity Index (FASI) (assessment of erythema, size, and extension);
 - Modified Nobel Scoring System (assessment of target lesions and non-target lesions response);

- Categorical lesion count using the following categories: (0) no lesion; (1) <25 lesions; (2) 25-50 lesions; (3) 51-75 lesions; (4) >75 lesions;
- Assessment of lesion elevation.
- Have the subject (or parent/guardian for subjects under the developmental age of 7 years) complete the subject self-assessment survey.
- Take a photograph of the angiofibroma according to the Standardized Operation Procedure (Appendix 2).
- Record any AEs.
- Inform Subjects that they may be approached to participate in future trials with this product.
- Dismiss the subject from the study.

7.3 Efficacy Assessments

Efficacy will be assessed using the Investigator's Global Assessment (IGA) of the facial skin lesions; the facial angiofibromas severity index (FASI), a composite score based on erythema, size, and lesion extension scores; time to and proportion of subjects with a 30% improvement of the composite score (FASI); lesion counts; proportion of subjects with at least 2-grade improvement in categorical lesion counts; proportion of subjects with at least 2-grade improvement in lesion elevation score; and proportion of subjects with at least 2-grade improvement in the subject self-assessment survey; overall response assessment of target lesions and non-target lesions including the size and color based on Modified Nobel Scoring System; proportion of subjects with at least Moderate Improvement on Modified Nobel Scoring System; and proportion of subjects with at least a 2-grade improvement on the Week 12 IGA. Photographs will be taken of the involved area for documentation purposes at clinic visits.

7.3.1 Primary Efficacy Assessment: Investigator's Global Assessment

The investigator will perform the IGA at Screening, Visit 2 (Baseline), Visit 3 (Week 4), Visit 5 (Week 12), Visit 6 (Week 16), Visit 8 (Week 24) and Early Withdrawal. The scale in [Table 7-1](#) will be used; the IGA was developed based on discussion with FDA during the PIND meeting, the agency's guidance for Acne Vulgaris and recent FDA approved products (i.e., Mirvaso):

Reference: <http://www.fda.gov/downloads/Drugs/.../Guidances/UCM071292.pdf>

Table 7-1 Investigator's Global Assessment (IGA)

Description	Grade	Disease Status
Clear	0	Clear skin with no signs of erythema and no disease related lesions
Almost clear	1	Slight redness with few disease related lesions,
Mild	2	Greater than Grade 1; definite redness with scattered, some disease related lesions
Moderate	3	Greater than Grade 2; marked redness, concentrated, many disease related lesions
Severe	4	Greater than Grade 3; Very bright redness, confluent, highly concentrated disease related lesions
Very severe	5	Greater than Grade 4; fiery redness, very extensive disease related lesions covering very large area of the face

7.3.2 Secondary Efficacy Assessment: Facial Angiofibroma Severity Index (FASI)

At study visits (Visit 1 through Visit 3, Visit 5 Visit 8 and Early Termination), the investigator will grade the treatment area for erythema, average size, and degree of involved skin (lesion extension). The grades for erythema, size, and extension are presented in [Table 7-2](#). A composite score, the Facial Angiofibromas Severity Index (FASI), will be derived from these measurements.

Table 7-2 Scoring for Erythema, Size, and Extension

Score	Description
Erythema	
0	Clear skin with no signs of erythema
1	Almost clear; slight redness
2	Mild erythema; definite redness
3	Moderate erythema; marked redness
4	Severe erythema; very bright redness
Size	
0	No lesions
1	Few lesions, average lesion size \leq 2mm
2	Scattered, some lesions, average lesion size >2 to \leq 5mm
3	Concentrated, many lesions, average lesion size >5mm to \leq 10mm
4	Confluent, highly concentrated lesions
Extension	
0	No lesions
2	\leq 50% of the cheek surface
3	> 50% of the cheek surface

7.3.3 Secondary Efficacy Assessment: Lesion Count

At Visit 1 through Visit 3, Visit 5 Visit 8 and Early Termination the investigator will perform a lesion count, based on the categories presented in [Table 7-3](#).

Table 7-3 Lesion Count Categories

Score	Description
0	No lesion
1	< 25 lesions
2	25 to 50 lesions
3	51 to 75 lesions
4	>75 lesions

7.3.4 Secondary Efficacy Assessment: Lesion Elevation

At Visit 1 through Visit 3, Visit 5, Visit 8 and Early Termination, the investigator will assess the degree of lesion elevation in the area of interest.

Table 7-4 Lesion Elevation Categories

Score	Description
0	No elevation over normal skin
1	Possible but difficult to ascertain whether there is slight elevation above normal skin
2	Slight but definite elevation
3	Moderate elevation
4	Marked elevation

7.3.5 Secondary Efficacy Assessment: Subject Self-Assessment Survey

Subjects, or their parent/guardian for subjects under the developmental age of 7 years, will be asked to complete the subject self-assessment survey, displayed in [Table 7-5](#), at each clinic visit.

Table 7-5 Subject Self-Assessment Survey

Circle the number that best describes the status of your facial bumps RIGHT NOW.	
0	No redness and no disease-related bumps
1	Very mild redness with few very small bumps
2	Mild redness with some scattered bumps
3	Moderate redness with many small and medium sized bumps
4	Severe redness with numerous small, medium and large sized bumps

7.3.6 Secondary Efficacy Assessment: Modified Nobel Scoring System

At study visits (Visit 2, Visit 3, Visit 5, Visit 6, Visit 8 and Early Termination), the investigator will perform response assessment of target lesions and non-target lesions including the size and color based on Modified Nobel Scoring System.

[figure not shown]
7.3.6.1 Response for Target Lesions

Before scoring, the investigator should choose 3 of the largest isolated lesions as target lesions, then measure both the Volume and Color of each lesion as indicated below, using provided label:

- Measure lesion dimensions to the nearest 0.1 mm;
- Assess color of the lesion using provided color panel;
- Take a close-up photo of each lesion, including the color panel and mm scale label on the same plane;
- Volume of one lesion = (long diameter) x (short diameter) x (short diameter)/2.

Color scale of 1-6 as displayed in [Table 7-6](#):

Table 7-6 Color Scale for Color Assessment

Level	Status of Reddishness	Pantone® Color Sample Remark
1	As dark as or paler than Pantone® 489C	
2	As dark as or paler than Pantone® 486C	
3	As dark as or paler than Pantone® 7416C	
4	As dark as or paler than Pantone® 485C	
5	As dark as or paler than Pantone® 704C	
6	Darker than Pantone® 704C	-

The investigator will calculate total volume and total color score of all 3 target lesions at baseline visit and each post-baseline visit, and calculate the percent change from baseline in total volume and percent change from baseline in total color then average these two percent change from baseline values to give improvement score. The scale in [Table 7-7](#) will be used for response assessment of target lesions.

Table 7-7 Scale for Response Assessment of Target Lesions

Score	Response Category	Criterion
-1	Worsened	20% or more increase
0	Unchanged	Less than 20% reduction
1	Slight improvement	$\geq 20\% - < 50\%$ reduction
2	Moderate improvement	$\geq 50\% - < 75\%$ reduction
3	Remarkable improvement	$\geq 75\%$ reduction

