Rapamycin (or sirolimus) binds to and inhibits the activity of mTOR. Everolimus is a derivative of rapamycin that acts in a similar fashion to rapamycin.⁷ There are a number of reports in the literature of small case studies in which sirolimus or everolimus was used to treat facial angiofibromas.⁸⁻¹⁸ In these reports, improvement in the facial skin tumors was noted in all cases, although complete clearance of the skin tumors is not possible due to the underlying mechanism of the disease (i.e., the aberrant activation of mTOR) and the treatment was well tolerated. Salido et al¹⁴ reported that subjects with TSC-associated facial angiofibroma treated with topical sirolimus ointment (0.4%) once daily, 3 times a week for 9 months showed improvement in erythema and in the size and extension of tumors with no local or systemic adverse events.

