4.2 Study Endpoints

The primary efficacy endpoint will be the proportion of subjects with a clinical response of treatment success at Week 12. Treatment success is defined as:

- At least a 2-grade improvement on the Week 12 Investigator Global Assessment (IGA) of the facial skin lesions assessed by the investigator.

Secondary efficacy endpoints will be the following:

- The proportion of subjects with an investigator assessed IGA score of clear or almost clear with at least a 2-grade improvement on the Week 12 IGA of the facial skin lesions;
- The proportion of subjects with at least 30% improvement at Week 12 as compared to Baseline in the Facial Angiofibromas Severity Index (FASI) score, which is based on lesion erythema, size, and extension ([Salido et.al. 2012](#));²⁰
- The time to reach at least 30% improvement from Baseline in the FASI score for angiofibroma severity;
- The proportion of subjects with at least 2-grade improvement at Week 12 as compared to Baseline in categorical lesion counts (scored as follows: No lesion = 0; <25 lesions = 1; 25-50 lesions = 2; 51-75 lesions = 3, >75 lesions = 4);
- The proportion of subjects with at least 2-grade improvement at Week 12 as compared to Baseline in lesion elevation score;
- The proportion of subjects with at least 2-grade improvement at Week 12 as compared to Baseline in the subject self-assessment survey;
- Overall Response of angiofibroma assessed by the investigator at Week 12 as compared to baseline based on Modified Nobel Scoring System;
- Overall Response of angiofibroma assessed by the IRC at Week 12 as compared to baseline based on Modified Nobel Scoring System;
- The proportion of subjects with at least Moderate Improvement (a score of 2) on Modified Nobel Scoring System assessed by the investigator at Week 12;
- The proportion of subjects with at least Moderate Improvement (a score of 2) on Modified Nobel Scoring System assessed by the IRC at Week 12;
- The proportion of subjects with at least a 2-grade improvement on the Week 12 Investigator Global Assessment (IGA) of the facial skin lesions assessed by the IRC.

Blood samples for pharmacokinetic analyses will be collected to confirm systemic pharmacokinetics.

Safety will be assessed through the monitoring of AEs, laboratory test results, vital signs, and physical examinations.

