5.2 Inclusion Criteria

Subjects must meet all of the following criteria to be eligible for participation in the study:

1. Generally healthy males or non-pregnant females aged 2 to 21 years, inclusive, at the time of screening.
2. Diagnosis of TSC with visible facial angiofibromas of at least grade 3 up to grade 5, inclusive, based on the IGA, at the time of screening.
3. Subjects with 3 or more isolated, measurable lesions of facial angiofibroma, with color grading score ≥ 2 for each of the 3 lesions.
4. Females of childbearing potential must have a negative urine pregnancy test (or a negative serum pregnancy test if a urine pregnancy test cannot be obtained) (For China, different pregnancy test procedure would be followed) and if sexually active or become sexually active during the study, must agree to use an effective form of birth control for the duration of the study. Females using oral contraceptives must also use a barrier method of contraception during the study. Sexually active male subjects and/or their female partners should also use appropriate contraception.

Effective contraception is defined as follows:

- Oral/implant/injectable/transdermal/estrogenic vaginal ring contraceptives, intrauterine device, condom with spermicide, diaphragm with spermicide.
- Abstinence or partner's vasectomy are acceptable if the female agrees to implement one of the other acceptable methods of birth control if her partner changes.

5. The subject and/or their parent or guardian must be willing and able to provide written informed consent/assent.
6. Willing and able to comply with all trial requirements.

7. Subject or parent/guardian must be able to complete the subject self-assessment survey and subject diary in English or another language into which the documents have been officially translated.
8. Subjects should be in good general health based on the subject's medical history, physical exam, and impression of the study doctor.

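### Modified Nobel target lesions are chosen without a colour condition, so the scored lesions need not be the colour ≥2 lesions that qualified the subject, and pale targets cap the attainable score (minor)

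*Combined protocol and SAP*

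**What the plan says.** Inclusion criterion 3 (section 5.2) admits "Subjects with 3 or more isolated, measurable lesions of facial angiofibroma, with color grading score ≥ 2 for each of the 3 lesions". It does not call these the target lesions and does not require them to be the largest.

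Section 7.3.6.1 sets the targets for the Modified Nobel score: "the investigator should choose 3 of the largest isolated lesions as target lesions". Size and isolation are the only conditions, and there is no reference back to criterion 3.

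The same section gives a "Color scale of 1-6 as displayed in" Table 7-6. The lowest level, 1, is defined as "As dark as or paler than Pantone® 489C", so there is no level 0. The investigator takes the percent change from baseline in total volume and in total colour of the three targets, and is to "then average these two percent change from baseline values to give improvement score". Table 7-7 makes a mean reduction of at least 20% Slight (score 1) and of at least 50% Moderate (score 2).

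Section 7.3.6.3 adds a non-target score of −1, 0 or +1, and an overall score of 2 is Moderate. One endpoint built on this in section 4.2 is "The proportion of subjects with at least Moderate Improvement (a score of 2) on Modified Nobel Scoring System assessed by the investigator at Week 12". An IRC version of that proportion, and overall response by investigator and by IRC, make four secondary endpoints.

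**The concern.** A subject can qualify on three smaller red lesions and be scored on three larger pale ones. A lesion that starts at level 1 cannot improve in colour, yet colour carries half the weight of the target score. The paler the targets, the more volume loss is needed to reach the same response category.

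A subject on sirolimus who would have responded on the qualifying lesions could then be counted as a non-responder. With 45 subjects randomised 1:1:1, an arm has 45/3 = 15 subjects, so one such subject is 1/15 = 6.7 percentage points of that arm's rate. The figure applies only if that subject would otherwise have responded.

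The schedule does not close the gap. Eligibility is reviewed at Screening and Baseline, and the Modified Nobel measurements start at Baseline (Table 1-1, section 7.2.2), but no step requires the qualifying and the scored lesions to be the same.

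**Working it through.** The plan gives no figure to reproduce here. Section 8.2 states that the sample size has no statistical rationale, and no response rate is assumed for this score. The check is direct arithmetic on the scoring rule.

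**Inputs**
- Colour floor: level 1 per lesion (Table 7-6), so three targets cannot total less than 3.
- Target score: mean of the percent reductions in total volume and total colour (7.3.6.1).
- Thresholds: 20% for Slight, 50% for Moderate (Table 7-7).
- Volume: long diameter × short diameter squared / 2 (7.3.6.1), cubic in linear size.

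**Formulas**
- With baseline colour total C, the largest possible colour reduction is (C − 3)/C.
- The volume reduction needed for a mean of T is V = 2T − (C − 3)/C. For Moderate (T = 50%) this simplifies to V = 3/C.
- If all dimensions shrink in proportion, the matching linear shrinkage is 1 − (1 − V)^(1/3).

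**Volume loss needed for target Moderate, every target reaching level 1**

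| Baseline colours | C | Largest colour reduction | Volume loss needed | Linear shrinkage |
|---|---|---|---|---|
| 1,1,1 | 3 | 0% | 100% | 100% |
| 1,1,2 | 4 | 25% | 75% | 37% |
| 1,2,2 | 5 | 40% | 60% | 26% |
| 2,2,2 | 6 | 50% | 50% | 21% |
| 1,1,4 | 6 | 50% | 50% | 21% |
| 1,3,3 | 7 | 57% | 43% | 17% |

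For 1,1,1, a 99% volume loss gives a mean of (99 + 0)/2 = 49.5%, which is still Slight.

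**The other route to overall Moderate.** Target Slight (1) plus non-target remarkable improvement (+1) also gives 2. For 1,1,1, Slight needs V = 2 × 20% − 0 = 40%, about 16% linear shrinkage. The non-target +1 needs overall colour down by at least 2 grades and overall size or extent down by 75% (Table 7-8), which is demanding.

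**Reading the table.** These are best-case figures: they show what can be reached, not what to expect. The 1,1,4 row, for instance, needs the level 4 lesion to fall three levels.

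**With targets restricted to colour level 2 or more.** The palest possible set is 2,2,2, so the largest volume loss needed at best-case colour falls from 100% to 50%. Criterion 3 guarantees that every eligible subject has three such lesions, so the restricted rule can always be applied.

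**The case against.** The strongest reply is that criterion 3 already describes the targets. The target set is the only set of three lesions that the protocol measures and colour-grades one by one, and its first measurement is at Baseline, where eligibility is checked again before randomisation. The wording of 7.3.6.1 also leaves some choice among the larger lesions. This stands in part: the defect is an unstated link, not a contradiction. But the text does not make the link, and up to 15 sites could apply it differently.

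Second, entry requires IGA grade 3 to 5, which means marked redness or worse, so three level 1 lesions among the largest should be uncommon. This stands. IGA rates the whole face, so it makes the case unlikely without excluding it.

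Third, targets are chosen at Baseline under the blind, the endpoints are secondary, and section 8.2 calls the study exploratory. All of this stands and limits the severity.

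A reader might infer that at least Moderate Improvement is almost unreachable for any subject with a pale target. The documents do not support that: 1,1,2 and 1,2,2 need linear shrinkage of about 37% and 26%, and redder companions remove the limit.

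A reader might also infer that Remarkable is closed to subjects at the minimum eligible colour, because 2,2,2 would need total volume loss and section 2.1 says "complete clearance of the skin tumors is not possible due to the underlying mechanism of the disease". That does not follow either. Overall Remarkable (score 3) can also come from target Moderate plus non-target +1. The section 2.1 remark concerns clearing the skin tumours in reported cases; it does not say that three individual lesions cannot resolve.

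**Conclusion.** The point holds as a minor gap. As written, the selection rule can score lesions that have little or no room to improve in colour. The volume loss needed for target Moderate then rises from 50% (2,2,2) to 60%, 75% or 100% as one, two or all three targets start at level 1 and the rest at level 2. Only 1,1,1 is close to unreachable through the targets.

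The figures assume that every target reaches level 1. The documents do not say how many subjects would have pale large lesions, so the effect on any arm's rate cannot be calculated; it is probably small. Any loss is blinded and non-differential. The primary IGA endpoint is untouched. Whether the IRC would meet the same limit depends on a separate photographic work instruction (7.3.7.2) that is not among the documents. It is likely, since the close-up photographs are of the target lesions.

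**What to change.** In section 7.3.6.1, and in the IRC instruction, replace the selection rule with:

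> At Baseline choose the three largest isolated, measurable lesions with colour level ≥2 (the lesions that qualify the subject under inclusion criterion 3) and score these same lesions at every later visit.

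The cost is one sentence in each place, with no new measurement. The downside is that a larger pale lesion is sometimes passed over for a smaller red one, so the targets are not always the largest lesions on the face. The colour scale, the averaging and the response categories can stay as they are.
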